2.1 Structured trial summary

Public Title	Simvastatin in Progressive Multiple Sclerosis
Scientific Title	A double-blind, randomised, placebo-controlled multi-site study of high dose simvastatin treatment for progressive multiple sclerosis: impact on vascular perfusion and oxidative damage
Countries of Recruitment	United Kingdom
Health Condition(s) or Problem(s) Studied	Progressive Multiple Sclerosis
Objectives:	
The primary outcome ASL measured CBF will be compared between patients on simvastatin or placebo using multiple linear regressions at 16 weeks.
 
Secondary objectives include: A. MRI: NODDI, myelin loss or changes, Grey matter atrophy and Number of new or enlarging T2 lesions. B. Clinical outcomes: EDSS, 25 foot timed walk, 9 hole peg test, MSIS-29v2, and MSWSv2. C. Retinal imaging parameters: vascular imaging, relative retinal vessel oxygen saturation and vessel width, non-invasive wide-field maps of both retinal (superficial and deep) and choroidal vascular plexuses, high-resolution retinal neuronal structure and SDOCT. D. Health Economic outcomes: EQ5D5L. E. Exploratory outcomes include immune parameters, and biomarkers. F. Frontal executive functioning will be assessed using the Frontal Assessment Battery (FAB) and other neuropsychological assessments (SDMT instrument).

Type of trial:	Phase II, double-blind, randomised, parallel group, single-site trial in progressive multiple sclerosis.
Trial design and methods:	40 subjects will be randomised double blind 1:1 to simvastatin or placebo. Simvastatin will be started at 40mg once daily for one month increasing to 80mg daily for a further three months with matching placebo based

on a satisfactory safety assessment at one month. The primary outcome ASL measured CBF and BAT will be compared between patients on simvastatin or placebo using multiple linear regressions with CBF or BAT at 16 weeks as the dependent variable, and age, gender, CBT or BAT at baseline and treatment group entered as covariates.

Trial duration per participant: Twenty-two weeks including follow-up (up to 17 weeks on treatment)

Estimated total trial duration: Two years

Planned trial sites: 2

Total number of participants planned: 40

Main inclusion/exclusion Criteria:

Trial Participant inclusion criteria

The following inclusion criteria must be met (answer yes) when assessing patient's eligibility onto the trial:

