21.1 Primary outcomes

A sophisticated magnetic resonance imaging (MRI) technique, called arterial spin labelling (ASL), will be employed to evaluate the effect of high dose statin on brain haemodynamics. Specifically, patients on statin or placebo will be subjected to multiple delay time ASL to quantify arterial hemodynamic parameter bolus arrival time (BAT) and cerebral blood flow (CBF) in normal-appearing white matter (NAWM) and deep gray matter as previously described (Paling et al., 2014). ASL is an MRI method that allows non-invasive measurement of CBF using inversion of arterial water spins as a tracer. In a recent study (Paling et al., 2014) the [name] team has demonstrated alteration in cerebral arterial hemodynamics in MS, in particular an increase in cerebral blood flow (CBF) in NAWM (14.4 ± 4.4 versus 10.1 ± 2.1 mL/100 g per min, $P < 0.001$), and a decrease in CBF in the deep gray matter (40.3 ± 12.0 versus 46.0 ± 5.7 mL/100 g/min, $P < 0.005$) in patients with MS compared with controls. As such, we expect ASL to be able to detect subtle changes in CBF between baseline, 16 and 20 weeks between placebo and simvastatin treated patients in the current study, including potential waning of the effects of the drug over time.

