22.3 Randomisation methods

This study will have a participant randomised design with equal allocation between treatment arms. Randomisation with a minimization algorithm will be used, using up to a maximum of four binary variables:

- gender

- binary age (≤ 55 />55 years old)
- binary disability (EDSS ≤ 5.0 />5.0)
- binary progressive clinical phenotype (SPMS/PPMS)

The cut-offs have been decided based on the literature: an age ≤ 55 years old was part of the inclusion criteria for the ORATORIO trial (ref: Montalban et al., NEJM 2016); in the same trial an EDSS score of 5.0 or lower was considered as 'less disabled', for which shorter disease durations were assumed/required to enter the trial (ref: Montalban et al., NEJM 2016). The study is exploratory and the number of subjects/arm is estimated based on established measures of within and between subject standard deviations using ASL, based on a large test-retest study (Petersen et al., 2010).

Randomisation will be performed by the PI or delegated member of the clinical investigating team at local sites using the web-based randomisation service, Sealed Envelope. A random sequence for study arm allocation will be computer generated by Sealed Envelope providing a unique trial identification code for each recruited participant.

Eligibility and consent will be verified before each patient is randomised. Study arm allocation into two treatment arms (1:1) will take into consideration these minimisation factors:

Randomisation with minimisation will ensure comparability of the two study arms, and prevent selection bias.

[figure not shown]
Sealed Envelope will generate unique identifiers for every active/placebo drug kit. The drug kit identification codes will be provided to Sealed Envelope and the Qualified Person (QP) at drug manufacturing site (Mode Pharma) who will ensure that trial drug and placebo packs are labelled appropriately, and that the trial team and participants remain blind to treatment allocation. At baseline, the investigator will enter the patient's unique trial identification code into the SealedEnvelope.com website which will then provide the drug identification code of the active/placebo drug kit to be dispensed. Sufficient number of simvastatin/placebo drug kits will be provided to ensure availability of adequately labelled kits for Pharmacy dispensing.

23. Statistical analysis plan

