23.3 Primary outcome analysis

The primary outcome ASL measured CBF will be compared between patients on simvastatin or placebo using multiple linear regressions at 16 weeks as the dependent variable, and age, gender or CBT at baseline and treatment group entered as covariates. Whenever the variable 'treatment group' is significant (at 5% significance level), it will be assumed that there is a treatment effect. The same models will be used to investigate the effect of simvastatin on the other imaging outcome measures.

Checks for model assumptions:

For all regression-type approaches, we will assess the normality of the residuals (of each one of the fitted models) through q-q plots. Residual homoscedasticity will be assessed through two-way scatter plots of the residuals over fitted values. Once we build the model with all possible predictors as explanatory variables, the assumption of the linear relationship between the dependent variable and each one of the predictors individually, given the presence of the other predictors, will be assessed through investigating different functional forms of the predictor and their impact on the R^2 of the model. The independence of observations will be always assumed.

Violations of model assumptions:

If the main assumption violated is that of homoscedasticity (i.e. there is residual heteroscedasticity), robust estimations of the standard errors (SE) of the regression parameters will be made, using the sandwich estimator of the SE. Whenever the residual distributions show a clear deviation from normality, bootstrap-based approaches will be used, with at least 1000 replication samples: bias-corrected and accelerated bootstrap-based 95% Confidence Intervals (95% CI) will be computed for each estimated parameter.

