- To collect health economic data (EQ5D5L) to inform future phase III trials.

- **Exploratory objectives:** to advance our understanding of the mechanisms of efficacy, and how vascular perfusion and oxidative damage is affected in progressive MS both in the presence and absence of simvastatin.

- To investigate phenotypic immune markers in whole blood to determine effect simvastatin has on immune function.
- To measure biomarkers of blood brain barrier dysfunction, vascular leakage and oxidative damage in participants treated with statins and placebo.
- To investigate levels of circulating cholesterol.

2. Statistical Analysis Plan:

- **Primary outcome analysis.** The ASL-measured CBF in white matter (), grey matter, deep grey matter, and thalamus will be compared between patients on simvastatin or placebo using *multiple linear regressions* at 16 weeks as the dependent variable, and age, gender or CBF at baseline and treatment group entered as covariates. Whenever the variable ‘treatment group’ is significant (at 5% significance level), it will be assumed that there is a treatment effect. The same models will be used to investigate the effect of simvastatin on the other imaging outcome measures.
- **Checks for model assumptions.** For all regression-type approaches, we will assess the normality of the residuals (of each one of the fitted models) through q-q plots. Residual homoscedasticity will be assessed through two-way scatter plots of the residuals over fitted values. Once we build the model with all possible predictors as explanatory variables, the assumption of the linear relationship between the dependent variable and each one of the predictors individually, given the presence of the other predictors, will be assessed through investigating different functional forms of the predictor and their impact on the R2 of the model. The independence of observations will be always assumed.
- **Violations of model assumptions.** If the main assumption violated is that of homoscedasticity (i.e. there is residual heteroscedasticity), robust estimations of the standard errors (SE) of the regression parameters will be made, using the sandwich estimator of the SE. Whenever the residual distributions show a clear deviation from normality, bootstrap-based approaches will be used, with at least 1000 replication samples: bias-corrected and accelerated bootstrap-based 95% Confidence Intervals (95% CI) will be computed for each estimated parameter.

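### The primary CBF model omits two of the four minimisation factors, 20 per arm covers 15% loss rather than the stated 20%, and the covariate sentence needs a wording correction

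*SAP*

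**What the plan says.** **Model.** SAP section 2 (Primary outcome analysis) covers white matter and "grey matter, deep grey matter, and thalamus will be compared between patients on simvastatin or placebo" by linear regression at 16 weeks, with "age, gender or CBF at baseline and treatment group entered as covariates". Protocol section 23.3 has the same sentence with a different abbreviation: "age, gender or CBT at baseline and treatment group entered as covariates". Protocol section 2.1 differs: "age, gender, CBT or BAT at baseline and treatment group entered as covariates". There, *or* separates the baseline values of two outcomes, because the same row says "The primary outcome ASL measured CBF and BAT will be compared between patients on simvastatin or placebo".

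**Allocation.** Protocol section 22.3 describes minimisation "using up to a maximum of four binary variables": gender, age (55 or under, over 55), EDSS (5.0 or under, over 5.0) and phenotype (SPMS, PPMS). The statistical row of section 2.1 still caps the number at three. Section 23.2 gives the minimisation variables as an example of covariates that the SAP would pre-specify. Protocol section 23.5 and the SAP's sensitivity paragraph add only that adjustment will be considered if a baseline imbalance appears.

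**Sample size.** Protocol sections 2.1 and 22.1 assume mean grey matter CBF of 40 mL/100g/min, SD 12, a 30% change, 80% power and 5% significance. This gives 17 per group, raised to 20 for drop-out and imaging failure, with 20% as the figure shown. Section 22.1 adds that regression to the mean, not allowed for, would reduce the number needed. It gives no correlation.

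**The concern.** There are three separate points about the primary analysis and the power behind it.

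1. **Omitted factors.** Minimisation makes the arms more alike on EDSS group and phenotype than simple randomisation would. If these factors predict CBF and the model ignores them, their variance stays in the residual although the allocation has already balanced most of it between arms. The treatment estimate is unbiased, but its standard error is overstated and the test rejects too seldom under the null.
2. **Loss allowance.** The step from 17 to 20 does not match the stated 20%, so the plan claims more protection against missing scans than it has.
3. **Wording.** The *or* in SAP section 2 and protocol section 23.3 can be read as a choice between gender and baseline CBF. Baseline CBF is likely to be the covariate that adds most precision, so its place in the primary model should not be open to interpretation.

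**Working it through.** **Reproducing 17 per arm.** The difference is 0.30 × 40 = 12 and the SD is 12, so the standardised effect is 12/12 = 1. A two-sided 5% t-test at 80% power needs n = 16.71, so 17, as stated. The protocol does not state sidedness; one-sided (normal approximation) would give 13. Power is 80.7% at 17 per arm and 78.1% at 16.

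**Loss allowance.**
- Number needed for 20% loss: 17/(1 − 0.20) = 21.25, so 22 per arm.
- Loss that 20 per arm absorbs: 1 − 17/20 = 15%.
- Evaluable after 20% loss: 20 × 0.80 = 16 per arm, power 78.1%.
- Possible origins of 20: 17 × 1.2 = 20.4 rounded down, or the normal-approximation n of 16 (15.70 rounded up) with 16/0.8 = 20. The documents do not say which, and neither agrees with 17 and a 20% loss.

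**Does covariate adjustment cover the shortfall?** This was simulated with 40 patients minimised on four binary factors, 8 lost at random, SD 12 at both visits and a true difference of 12. Assumed, because the documents do not give them: 50% prevalence of each factor, assignment probability 0.8, continuous age, and baseline to week-16 correlation r. In this run the factors have no effect on CBF. There were 40,000 trials per setting.

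| r (assumed) | Power: treatment, baseline CBF, age, gender | Power: the same plus EDSS group and phenotype |
|---|---|---|
| 0 | 74.8% | 73.1% |
| 0.3 | 78.6% | 76.7% |
| 0.35 | 79.9% | 78.2% |
| 0.4 | 81.2% | 79.8% |
| 0.5 | 85.7% | 84.3% |
| 0.7 | 95.6% | 94.7% |

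Power reaches 80% at r of about 0.35 with the present covariates and about 0.4 with six terms.

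**Cost of omitting EDSS group and phenotype.** Same design, r = 0.5, 20,000 trials per setting. The share of remaining variance that the two factors explain is assumed.

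| Share explained | CI width, without ÷ with | Type I error without | Type I error with |
|---|---|---|---|
| 0% | 0.981 | – | – |
| 10% | 1.035 | 4.4% | 5.1% |
| 20% | 1.098 | 3.8% | 5.1% |
| 30% | 1.178 | 3.3% | 5.3% |

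With assignment probability 1.0, the ratios at 10, 20 and 30% are 1.039, 1.105 and 1.182, and type I error without the factors is 4.5, 3.6 and 3.0%. With age group in place of continuous age, the ratios are 1.035, 1.099 and 1.177. Further runs at smaller shares gave ratios of 0.99 at 2% and 1.005 at 5%, so the two factors begin to pay for themselves at roughly 4 to 5%.

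**Cost of the literal *or*.** Without baseline CBF, power is 76.0 to 76.5% whatever r is. CI half-width without and with it:
- r = 0.3: 8.785/8.550 = 1.027
- r = 0.5: 8.795/7.772 = 1.132
- r = 0.7: 8.800/6.410 = 1.373

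**The case against.** The case for leaving the plan alone has four parts.

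- **There is already a route into the model.** Both documents allow adjustment for an imbalanced variable, and section 23.2 offers the minimisation variables only as an example. This is true, but the fallback depends on the data and minimisation makes it unlikely to be used. It also addresses the wrong problem, since the overstated standard error comes from balance rather than imbalance.
- **The gain is unproven.** Omission cannot create false positives by bias, and a patient's own baseline CBF may already carry any stable effect of EDSS or phenotype. Below about 4 to 5% of remaining variance, the six-term model is slightly less precise. This stands, and it limits the size of the point. The costs are uneven, though: about 2% in width if the factors predict nothing, against 3 to 18% over the assumed 10 to 30%.
- **The loss shortfall is trivial.** Power is 78.1% against 80%, treatment discontinuers stay in follow-up, multiple imputation is planned, and a modest correlation restores the target. On size this is right. The stated percentage is still inconsistent with the protocol's own 17, and the reassurance depends on baseline CBF being in the model.
- **The *or* is plainly a slip.** Probably so: section 2.1 shows the intended form. The 3, 13 and 37% wider intervals therefore describe a reading that is unlikely to be meant and should not drive the priority of this point.

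**Conclusion.** All three points hold, and all are modest. The first matters most: the primary model should contain the factors that the trial allocates by, and EDSS group and phenotype are missing from every version without explanation. The result is a loss of precision and a conservative test if they are prognostic, not bias. The loss allowance is an arithmetic inconsistency that costs about 2 points of power before adjustment; it is not a failed design. The *or* is a probable drafting error that needs correcting because it sits in the sentence defining the primary model.

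The textual facts, the t-test figures and the 15% follow directly from the documents. The other magnitudes rest on the assumed correlation, variance explained, factor prevalence and assignment probability. The documents do not say how prognostic the two factors are or how strongly baseline and week-16 CBF correlate.

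**What to change.** 1. In SAP section 2 and protocol section 23.3, state the model once for each CBF region analysed: week-16 CBF on treatment group, baseline CBF in the same region, age (form stated, for example continuous), gender, EDSS group and phenotype. Remove the *or*, and correct the abbreviation for CBF in the protocol.
2. In protocol section 2.1, use the same covariates with the baseline value of the matching outcome. Sections 2.1 and 21.1 include BAT, while section 23.3 and the SAP model name only CBF; the sponsor should reconcile its status.
3. In the statistical row of section 2.1, change the number of minimisation variables from three to four, to match section 22.3.
4. In protocol sections 2.1 and 22.1, state that 20 per arm allows for 15% loss, and that 20% loss leaves 16 per arm with 78.1% power before covariate adjustment.

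The cost is wording in two documents and one restated planning figure, with no change in recruitment. EDSS group and phenotype are already needed to randomise each patient, so no new data are required. The downside is two degrees of freedom: about 2% in interval width and 1 to 2 points of power if the added factors predict nothing.

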3.2 Clinical data

This remarkable pleiotropic capacity for modulating the immune system and inflammation has prompted the clinical testing of statins for the treatment of RRMS and other inflammatory diseases (Vollmer et al., 2004; Neuhaus and Hartung, 2007; Paraskevas, 2008; Yuan et al., 2012; Young and Hopkins, 2013). In one such study in 30 patients with RRMS, simvastatin (80mg) taken over 6 months reduced the number of brain lesions by 40%, although no change in disability scores was observed over this short study period (Vollmer et al., 2004). Other studies, however, have failed to demonstrate any significant clinical improvement in RRMS following statin treatment alone or in combination with other disease modifying drugs. Nevertheless, it should be noted that none of the studies so far have been sufficiently powered, rendering definitive conclusions impossible.

Whilst there is a clear-cut rationale for using statins for the treatment of RRMS, in SPMS/PPMS there is less obvious justification, as disease progression in the absence of new plaque formation is thought to be due predominantly to neurodegeneration (or neuronal loss). This results from several mechanisms, including microglia activation, chronic oxidative injury, accumulation of mitochondrial damage in axons, and age-related iron accumulation in the human brain (Mahad et al., 2015). Whereas large scale inflammatory lesions rarely occur at this stage of the disease, inflammation is prominent in progressive MS, where it is found throughout the grey and white matter, and in the meninges, with its most severe form being represented by the ectopic follicles that contribute to grey matter damage (Kutzelnigg et al., 2005; Magliozzi et al., 2007). This suggested that given their Immunomodulatory / anti-inflammatory actions, statins might still provide some benefit in SPMS/PPMS. Nonetheless, neuronal loss is regarded as the key pathological feature, which raised the question whether statins also possess neuroprotective properties. Several lines of evidence suggest this may be the case.

Firstly, statins are increasingly seen as vasculoprotective (Greenwood and Mason, 2007; Liao, 2002; Mason, 2003; Haendeler et al., 2004; Antonopoulos et al., 2012) with a capacity to improve vascular perfusion (Endres et al., 1998; Giannopoulos et al.,

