(3) Grey matter atrophy, which is significantly associated with long-term disability in SPMS (Fisniku et al., 2008) and correlates with physical disability better than white matter atrophy (Roosendaal et al., 2011). Our previous simvastatin trial demonstrated a reduction of 43% in the annualized rate of whole brain atrophy associated with the drug (Chataway et al., 2014), but the rate of grey matter atrophy was not assessed. The recent Lamotrigine trial in patients with SPMS demonstrated that the grey matter atrophy was greater than white matter atrophy (-1.18% per year vs. 0.12% per year), and was the only atrophy measure that correlated with clinical changes; in addition, no pseudo-atrophy was seen in the grey matter (Kapoor et al., 2010). Total and regional grey matter volumes, including thalamic volumes, will be calculated, and changes in

volumes over time using longitudinal VBM will be investigated.

Atrophy measures will be performed at baseline 16 and 20 weeks to assess the rate of atrophy; the extra time point added after the end of the study (20 weeks) when patients are off treatment will allow us to take into account a possible reduced volume in patients on treatment which results from pseudo-atrophy, rather than lack of neuroprotective effects of simvastatin. With regard to the atrophy calculation, T2 and T1 weighted conventional scans will be also acquired to perform the lesion-filling technique that reduces the impact of white matter lesions on grey matter volume (Chard et al., 2010).

(4) Number of new or enlarging T2 lesions, as surrogate markers for the inflammatory process, and number of new hypo-intense lesions seen on T1 weighted spin-echo, as a marker of tissue destruction.

This part of the study will be led by [name], NMR Unit, UCL Institute of Neurology.

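### New-lesion counts have no baseline value, so the shared imaging regression cannot be fitted to them as written, and the plan's bootstrap fallback inflates false positives

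*SAP*

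**What the plan says.** For CBF, SAP section 2 specifies multiple linear regression of the week-16 value, with "age, gender or CBF at baseline and treatment group entered as covariates". A treatment term significant at 5% is to be taken as a treatment effect. The next sentence extends the method: "The same models will be used to investigate the effect of simvastatin on the other imaging outcome measures". Protocol 23.3 carries the same sentence.

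Protocol 21.2.4.1, item (4), lists among the MRI measures: "Number of new or enlarging T2 lesions, as surrogate markers for the inflammatory process, and number of new hypo-intense lesions seen on T1 weighted spin-echo". The T2 count also appears among the secondary objectives in protocol 2.1 ("Grey matter atrophy and Number of new or enlarging T2 lesions"). The SAP does not name either count, and no other section of either document gives a method for them.

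The SAP has two contingencies. For unequal residual variance: "robust estimations of the standard errors (SE) of the regression parameters will be made, using the sandwich estimator of the SE". For non-normal residuals, judged from q-q plots: "Whenever the residual distributions show a clear deviation from normality, bootstrap-based approaches will be used, with at least 1000 replication samples", with bias-corrected and accelerated (BCa) 95% intervals.

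**The concern.** A new or enlarging lesion is recognised by comparing a later scan with the baseline scan. At baseline the count is not zero or missing; it is undefined. A rule that reuses a model with a baseline covariate therefore cannot be followed for these outcomes. Someone must later choose a substitute covariate or drop the term, and must decide how to handle a skewed count. Protocol 23.2 promises that methods and covariates will be set well before the data are seen.

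The contingency is the larger problem. Counts that are mostly zero, with a few higher values, will not look normal on a q-q plot, so the likely route is the bootstrap. With few patients and few lesions, BCa intervals tend to be too short. Because a significant treatment term is read as an effect, a fallback meant to protect the analysis could produce a false claim about lesion activity in a trial designed to explain mechanism.

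**Working it through.** **1. Can the model be fitted?** The regression needs an outcome at week 16 and a baseline covariate. For CBF both exist. For new or enlarging T2 lesions and new T1 lesions only the week-16 count exists. The one other literal reading, entering baseline CBF as the covariate for a lesion count, can be computed, but the documents give no reason for it.

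**2. Trial size.** The documents give no figure for lesion counts, so the only plan figure to reproduce is the number per arm (protocol 22.1: difference 30% of 40 = 12, SD 12, 80% power, 5% two-sided assumed). Normal approximation: 2 × (1.960 + 0.842)² × 12²/12² = 15.7, so 16. The t-based solution is 16.71, so 17, as stated. With 20 randomised per arm and 20% loss, 20 × 0.8 = 16. The analysed number is therefore about 16 to 20 per arm, and is not in dispute.

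**3. Assumed counts.** Mean 0.1 to 1.0 new lesions per patient by week 16, either Poisson or overdispersed negative binomial with size k = 0.5 (variance = μ + μ²/0.5). These are assumptions. The only support is verbal (protocol 3.2): "large scale inflammatory lesions rarely occur at this stage of the disease".

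**4. How often is an arm empty?** The chance that all n patients in an arm have no lesion is exp(−nμ) for Poisson and (k/(k+μ))^(kn) for negative binomial. At μ = 0.1 and n = 20, Poisson gives exp(−2) = 0.135, so exactly one empty arm has probability 2 × 0.135 × 0.865 = 0.23. At n = 16 with k = 0.5 the figures are (0.5/0.6)^8 = 0.233 and 2 × 0.233 × 0.767 = 0.36. Simulation gave 23-36% over these settings. The plan does not say what is done then.

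**5. Linear regression without the baseline term.** Treatment plus two covariates unrelated to outcome, 4000 trials per setting. The estimate has no material bias: for means 0.5 and 0.25 at 20 per arm it averaged −0.253 against a true −0.250. Across means 0.1 to 1.0, null rejection was 2.4-5.1% with ordinary standard errors and 0.8-5.2% with sandwich errors.

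**6. The bootstrap fallback.** BCa intervals with 1000 resamples, 600 trials per setting, no true effect. HC1 is one version of the sandwich estimator. Rejection of the null, %:

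| Per arm | Counts | Mean | Ordinary SE | Sandwich (HC1) | BCa |
|---|---|---|---|---|---|
| 16 | Poisson | 0.2 | 4.4 | 4.4 | 8.3 |
| 16 | Poisson | 0.5 | 4.3 | 4.8 | 3.8 |
| 16 | Poisson | 1.0 | 4.8 | 5.0 | 6.2 |
| 16 | k = 0.5 | 0.2 | 3.6 | 3.4 | 10.0 |
| 16 | k = 0.5 | 0.5 | 4.4 | 4.2 | 11.5 |
| 16 | k = 0.5 | 1.0 | 4.0 | 4.0 | 15.2 |
| 20 | Poisson | 0.2 | 4.6 | 4.9 | 8.8 |
| 20 | Poisson | 0.5 | 4.6 | 4.9 | 6.5 |
| 20 | Poisson | 1.0 | 4.9 | 5.2 | 8.0 |
| 20 | k = 0.5 | 0.2 | 4.7 | 4.4 | 11.2 |
| 20 | k = 0.5 | 0.5 | 3.5 | 3.4 | 10.3 |
| 20 | k = 0.5 | 1.0 | 5.1 | 5.0 | 10.2 |

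Eleven of the 12 BCa figures exceed 5%, and their average is 110.0/12 = 9.2%. The simulation error on a rate of 10% is √(0.1 × 0.9/600) = 1.2 points. A separate simulation at 17 per arm with age- and sex-type covariates and means 0.1 to 1.0 gave about 7-13.5%.

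**7. Candidate replacements.** A permutation test at 17 per arm rejected a true null in 0.5-4% of trials. A plain Poisson model is not safe: 12-28% for the overdispersed counts with mean 0.5 to 1.0. A negative binomial model at 17 per arm (k = 0.5 or 2) gave no usable result in 59-65% of trials at mean 0.1, 17-36% at 0.3, 9-23% at 0.5 and 1-9% at 1.0. Where counts were highest, its null rejection was 6.6-7.4%.

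**The case against.** The strongest defence is that these outcomes are peripheral and the damage is limited. The SAP never names them, protocol 5.5 omits them, 21.2.4.1 sits under other assessments, and 23.2 promises less detail for secondary analyses. The covariate wording is loose enough (it says *or*) that an analyst could simply omit the baseline term, and randomisation then makes the mean difference a fair estimate. All of this stands. It limits the importance of the point, but it does not supply the missing rule or repair the bootstrap.

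Several stronger readings are tempting and are not supported.

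- A reader might infer that linear regression cannot validly estimate a treatment effect on counts. Steps 4 and 5 show low information, not bias or an excess of false positives.
- A reader might object that the interval can imply a reduction of more than 100%, or that fitted values can fall below zero. The first mainly reflects few lesions in about 34 patients; the second does not bias the treatment coefficient.
- A reader might take protocol 3.2 to say that these counts will be mostly zero. It speaks of large-scale lesions, and goes on to say that inflammation is prominent in progressive MS. Sparsity is plausible but assumed.
- A reader might treat both counts as the trial's inflammation markers. The protocol calls new T1 lesions a marker of tissue destruction, and it studies immune effects through blood markers.
- A reader might extend the point to all imaging. The SAP treats retinal metrics separately.
- A reader might conclude that a negative binomial model should lead. Step 7 argues against that at this sample size.

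**Conclusion.** The point holds in limited form. The shared imaging model cannot be applied literally to the two new-lesion counts, and the plan gives no substitute covariate, count method or rule for an arm without lesions. The choice left open matters. Ordinary or sandwich inference without the baseline term keeps the false-positive rate near or below 5%. The BCa route, which a q-q plot of such data is likely to trigger, raises it to roughly 7-13% at about 17 per arm. In individual settings at 16 or 20 per arm it ran from 3.8% to 15.2%.

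These sizes rest on assumed means of 0.1 to 1.0 lesions per patient and on Poisson or negative binomial variation. The absence of a baseline value rests on the definition of the outcome alone. The outcomes are secondary or exploratory, and nothing here touches the CBF analysis or the sample size.

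**What to change.** In SAP section 2 and protocol 23.3, exclude the two lesion counts from the shared imaging model and add:

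- By arm, report the week-16 counts and the number and proportion of patients with at least one new or enlarging T2 lesion, and with at least one new T1 hypo-intense lesion.
- Compare arms with a permutation test of the lesion count. If adjustment is wanted, name baseline T2 lesion load as the covariate; protocol section 12 already plans to quantify lesion load. The test remains usable when one arm has no lesions.
- Give a negative binomial rate ratio, with log scan interval as offset, only as a descriptive estimate, and only when both arms have lesions and the model converges.
- Do not use the BCa bootstrap for these two outcomes.

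The cost is a few sentences and no new data. The result will be on a different scale from the other imaging measures. The permutation test is conservative, most clearly at very low counts (0.5% at the bottom of its simulated range). Power will be low in any case: at 20 per arm, linear regression detected a halving from a mean of 0.2 in only about 8-10% of trials. If allocation is already known to the analysts, the change should be reported as a deviation under protocol 23.7.
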